This research is necessary to assess the impact of familial and peer related factors on nicotine addiction among medical students in South Punjab. This will help design targeted interventions and preventive strategies to mitigate the increasing trend.

Objectives

To determine the influence of the family environment and familial relationships on nicotine dependence among medical students.

To assess the impact of peer pressure on nicotine use and dependence.

To determine whether a positive or negative family and peer environment affects the likelihood of developing nicotine addiction.

Study Design

Cross-sectional study

Participants

Inclusion Criteria: Student enrolled in medical colleges in South Punjab, willing to participate.

Exclusion Criteria:

Students who didn't give consent

Those who were absent

Uncooperative students

Methods

Data Collection Procedure

Data will be collected through a **structured, self-administered questionnaire** in English. The initial section of the questionnaire will collect **basic demographic information**, including **age, gender, medical college, and year of study**.

Assessment Tools

Nicotine Dependence

To assess nicotine dependence, the **Fagerström Test for Nicotine Dependence (FTND)**—a globally validated tool—will be used.¹⁴ This test includes **six questions** focusing on behaviors such as the **use of cigarettes, e-cigarettes, and other tobacco-containing products immediately after waking, smoking in prohibited areas, and difficulty in giving up the first session of the day**. It also inquires about **daily frequency** and whether the participant **smokes despite illness** (Table 1).

The FTND provides a **continuous score ranging from 0 to 10**, based on six items:

- **Three yes/no items** will be scored as 0 (**No**) and 1 (**Yes**),
- **Three multiple-choice items** will be scored from 0 to 3.

The total score will be used to classify nicotine dependence as follows:

- **0–2:** Very Low
- **3–4:** Low
- **5:** Moderate
- **6–7:** High
- **8–10:** Very High

Each question will offer specific response options that aid in categorizing dependence levels. **Reliability analysis** is expected to yield a **Cronbach's alpha of approximately 0.702**, indicating acceptable internal consistency, as reported in prior studies.

Family Functioning

Participants will also be provided with the **Family Assessment Device – General Functioning subscale (FAD-GF)**, which includes **12 questions** to evaluate overall family functioning (Table 2).¹⁵ Each item will be rated on a **4-point Likert scale**, ranging from 1 (**Strongly Agree**) to 4 (**Strongly Disagree**), with **negatively worded items reverse-coded** to maintain scoring consistency. Higher scores will reflect **poorer family functioning**.

A **cutoff mean score of 2.00** will be applied:

- **Mean score ≥ 2.00** will indicate **unhealthy or dysfunctional family functioning**,
- **Mean score < 2.00** will reflect **relatively healthy family functioning**.

The FAD-GF scale is expected to demonstrate a **Cronbach's alpha of approximately 0.736**, indicating acceptable internal consistency.

Peer Pressure

Peer pressure will be assessed using items adapted from **Subramaniam et al.** This scale includes **six yes/no questions** divided into **direct** and **indirect** peer pressure:

- **Three questions** will assess **direct** peer pressure,
- **Three questions** will assess **indirect** peer pressure.

Students answering '**yes**' to any question will be considered to have **experienced peer pressure**, while those who respond '**no**' to all questions will be categorized as **not experiencing peer pressure**.

Statistical Analysis Plan

Statistical analysis will be carried out using SPSS version 26. Descriptive statistics will be used to summarize demographic data, smoking status, peer pressure, and family functioning. A two-way analysis of variance (ANOVA) will be conducted to assess the interaction effects of family functioning and peer pressure on nicotine dependence. For group comparisons, an independent t-test will be performed between students with functional and dysfunctional families experiencing peer pressure. A Chi-square test will be used to examine associations between gender, year of study, peer pressure, and smoking status. Assumptions for normality and equal variances will be verified prior to applying parametric tests, and the level of statistical significance will be set at $p < 0.05$.

Ethical Approval

Ethical approval will be obtained from the Institutional Ethical Review Board (IERB), Nishtar Medical University, Multan, Pakistan, prior to data collection. The study will ensure that subjects participate on a voluntary and anonymous basis. Prior to participation, informed consent will be obtained from each participant.

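### The FTND item scoring as written runs from 0 to 12, which contradicts the stated 0–10 score and leaves totals of 11 and 12 without a dependence band

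*Combined protocol and SAP*

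**What the plan says.** All the scoring text is in the protocol under Methods, Assessment Tools, Nicotine Dependence.

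- The FTND has six items and yields a "continuous score ranging from 0 to 10".
- Three items are yes/no, scored 0 for no and 1 for yes.
- For the other three: "Three multiple-choice items will be scored from 0 to 3".
- Totals are sorted into five dependence bands. From the top down these are very high (8–10), high (6–7), moderate (5 only), low (3–4) and very low (0–2).
- On the response options, the section says only this: "Each question will offer specific response options that aid in categorizing dependence levels". It lists no options and gives no points for any single item. It refers to Table 1.

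The Statistical Analysis Plan section then uses a two-way ANOVA to "assess the interaction effects of family functioning and peer pressure on nicotine dependence". It does not say whether the outcome is the score or the band.

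**The concern.** The item rule and the stated range cannot both be right. This sentence is the only scoring rule in the available text for nicotine dependence, which is the outcome in the study title, the objectives and the ANOVA.

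The unclassifiable totals of 11 and 12 are the visible symptom. The larger risk is over-weighting. If an item that should carry fewer points is coded up to 3, ordinary totals rise as well. Many of those totals stay between 0 and 10, so a check on the total alone would pass them. The score and the bands would both be affected, so the problem arises whichever of them the ANOVA uses.

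**Working it through.** **Inputs** (all from the Nicotine Dependence section): six items; three scored 0/1; three scored 0 to 3; stated range 0–10; bands 0–2, 3–4, 5, 6–7, 8–10.

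**1. Try to reproduce the stated range.** The minimum is 0. The maximum is the sum of the item maxima:

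3×1 + 3×3 = 3 + 9 = 12.

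The stated maximum of 10 is not reproduced.

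**2. Find the excess.** Points available to the multiple-choice items on a 0–10 score: 10 − 3 = 7. Points assigned: 3×3 = 9. Excess: 9 − 7 = 2.

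**3. See which item maxima would fit.** With each multiple-choice maximum equal to 1, 2 or 3, only two sets sum to 7:

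| Multiple-choice maxima | Sum | Total with yes/no items |
|---|---|---|
| 3, 3, 1 | 7 | 10 |
| 3, 2, 2 | 7 | 10 |
| 3, 3, 3 (as written) | 9 | 12 |

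The section names five behaviours for six questions and gives no item points, so it does not show which set is intended.

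**4. Map totals to bands.** Assume each multiple-choice item can take the values 0, 1, 2 and 3. The rule then allows 2³ × 4³ = 8 × 64 = 512 response patterns. Six total 11 (one of the six items is one point below its maximum) and one totals 12. So 7 patterns have no band. This counts patterns; it does not estimate a proportion of students.

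**5. Bound the inflation if coded as written.** Under 3+3+1, one item can be over-scored by up to 3 − 1 = 2 points. Under 3+2+2, two items can each be over-scored by up to 3 − 2 = 1 point. Either way a student's total rises by between 0 and 2.

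**6. Illustrate the effect on bands.** A true total of 4 (low) becomes 5 (moderate) at +1 or 6 (high) at +2. Not every shift matters: a true total of 0 stays very low at +1 or +2, and a true total of 8 stays very high.

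**The case against.** **The sentence may give a span across the three items.** It does not say that each multiple-choice item runs from 0 to 3, whereas the Family Functioning section does say that each item is rated on its scale. Read as a span, with at least one item having a lower maximum, the sentence is compatible with 0–10. This reading is possible but not the natural one, because the parallel line on yes/no items gives a per-item range. On the span reading the text still does not say which item has the lower maximum.

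**Table 1 may already hold the correct points.** This stands as a limit on the consequences. If Table 1 sums to 10 and is what gets coded, the data will be scored correctly and only the sentence needs correcting. The sentence would still contradict the range and bands beside it. The citation given for the instrument does not help, since it is number 14 and the reference list ends at 10.

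**Inflation is conditional.** An item with fewer than four options, coded consecutively from 0, never reaches 3 and inflates nothing. That is correct: inflation requires the 0-to-3 rule actually to be applied to an item meant to carry fewer points. The pattern count likewise rests on an assumption about response options that the documents do not give.

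**The split of items may be wrong instead.** Four two-option items and two items scored 0–3 also give 4×1 + 2×3 = 10. This contradicts the plan's own three/three split, so it is another way in which the section would be wrong. Its item maxima are those of the 3+3+1 case with one item relabelled, so an item-by-item list of points settles it too.

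**Conclusion.** The concern holds: the scoring rule is wrong as written. On its plain reading the maximum is 12 against the stated 10, the multiple-choice items carry 9 points against the 7 available, and totals of 11 and 12 have no band. No cap, exception or item key in the available text resolves this.

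The range and the bands agree with each other, so the fault most likely lies in the line on multiple-choice items. Confidence in the arithmetic is high. Any effect on results depends on the sentence, and not a correct Table 1, being what is coded; in that case the inflation is 0 to 2 points per student. The documents do not allow the number of affected students or the effect on the ANOVA to be computed. This should be fixed before scoring.

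**What to change.** 1. Replace the sentence on multiple-choice items with a list of the six items, each with its response options and points, taken from the instrument. Under the plan's three/three split the multiple-choice maxima must sum to 7; in any case the six maxima must sum to 10.
2. Reconcile that list with Table 1 so that the two agree. If the instrument's item types differ from three/three, correct that statement too.
3. Keep the five bands. They cover every total from 0 to 10.
4. In SPSS, check the range of each item against its listed maximum and confirm that no total exceeds 10. The item checks are essential, because an inflated total can still lie within 0–10.

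The cost is a few lines of protocol text and a recode with range checks. No new data are needed, provided item-level responses are kept.

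### Neither analysis of nicotine dependence adjusts for any demographic variable, although age, gender, college and year of study are collected

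*Combined protocol and SAP*

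**What the plan says.** The design is given as "Cross-sectional study". Under Data Collection Procedure, the questionnaire opens with "age, gender, medical college, and year of study".

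The Statistical Analysis Plan then lists four analyses:

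- Descriptive: "Descriptive statistics will be used to summarize demographic data, smoking status, peer pressure, and family functioning".
- Dependence, both exposures: "A two-way analysis of variance (ANOVA) will be conducted to assess the interaction effects of family functioning and peer pressure on nicotine dependence".
- Family comparison: "an independent t-test will be performed between students with functional and dysfunctional families experiencing peer pressure". The outcome of this test is not named; I take it to be nicotine dependence.
- Associations: "A Chi-square test will be used to examine associations between gender, year of study, peer pressure, and smoking status".

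No covariate, regression model, stratification or other adjustment appears anywhere in the document. Gender and year of study enter only the chi-square analysis. Age and medical college enter no named inferential analysis.

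The Objectives include "To assess the impact of peer pressure on nicotine use and dependence" and "To determine whether a positive or negative family and peer environment affects the likelihood of developing nicotine addiction".

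**The concern.** This is an observational survey. Students with and without peer pressure, or from functional and dysfunctional families, may differ in gender, age, seniority and college. The two-way ANOVA adjusts each exposure for the other, and the t-test holds peer pressure fixed, but neither removes a demographic difference.

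If, say, men report more peer pressure and also score higher on the Fagerström test, part of the gender difference will be read as an effect of peer pressure. The objectives are worded as questions about effects, and the main-effect contrasts and the t-test are the only planned analyses of dependence that could answer them. Those are the estimates that an omitted confounder distorts.

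The plan itself will examine whether gender and year are related to peer pressure and to smoking status, so it treats such links as possible. It then leaves both variables out of the dependence analysis.

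**Working it through.** **Inputs.** The documents state no sample size, SD, gender mix or effect size, so there is no planned figure to reproduce. Everything below is assumed and serves only to show what the omission could do. The 5% level is from the SAP; I take the tests as two-sided, which the SAP does not state. The assumptions are:

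- half the students are male;
- the score is 3 + b × male + normal error with SD 2, where b is the gender effect in points;
- peer pressure (P) and dysfunctional family (F) have no true effect and are independent given gender.

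**Bias formula.** Bias in an unadjusted mean difference = b × (male share in one group − male share in the other).

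**Setting A: b = 1; P is 60% in men and 40% in women; F is unrelated to gender.**

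- The male share is 0.6 with peer pressure and 0.4 without, so the peer bias is 1 × (0.6 − 0.4) = 0.20 points. The bias is 0 for family, the t-test and the interaction.
- Score variance within a peer group is 4 + 0.6 × 0.4 = 4.24.
- At N = 400 (200 per group), SE = √(4.24 × 2/200) = 0.206 and 0.20/0.206 = 0.97. The rejection probability is Φ(0.97 − 1.96) + Φ(−0.97 − 1.96) ≈ 0.16.

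**Setting B: as A, but F is also 60% in men and 40% in women.**

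- Male share with P and F both present: 0.36/(0.36 + 0.16) = 0.692. With exactly one present: 0.24/(0.24 + 0.24) = 0.5. With neither: 0.16/(0.16 + 0.36) = 0.308.
- Bias for each main effect: [(0.692 + 0.5) − (0.5 + 0.308)]/2 = 0.192.
- Bias for the t-test among peer-pressured students: 0.692 − 0.5 = 0.192.
- Bias for the interaction: 0.692 − 0.5 − 0.5 + 0.308 = 0.

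**Setting C: weak confounding, b = 0.5; 55% against 45%.** Bias = 0.5 × 0.10 = 0.05 points.

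**Rejection rates with no true effect** (Monte Carlo, 10,000–20,000 samples per setting; a nominal test should give 5%):

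| Setting and test | N = 200 | N = 400 | N = 600 |
|---|---|---|---|
| A, peer main effect | 10% | 16–17% | 22–23% |
| A, family effect, t-test, interaction | about 5% | about 5% | about 5% |
| B, each main effect | 10% | 15% | 21% |
| B, t-test | 8% | 10% | 13% |
| B, interaction | 5% | 5% | 5% |
| C, confounded main effect | 5–6% | 5–6% | 5–6% |

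With gender added to the model, the rates in A and B return to about 5%. In A at N = 400 it matters little whether SD 2 is within gender (16.5%) or overall (17.1%).

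**Wider range.** Write g for the confounder's effect in points and d for the difference in its prevalence between the compared groups. Take SD 2, g from 0.5 to 2, d from 0.1 to 0.3, and 50 to 200 students per group. The bias g × d then runs from 0.05 to 0.60 points, and the rejection rate of a simple two-group comparison from 5.2% to 85%. A middle case (g = 1, d = 0.2, 100 per group) gives bias 0.20 and 10.9%.

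**The case against.** The strongest reply is that the SAP directs the ANOVA at the interaction, which is the test least affected. That is correct, and it limits the point to the main effects and the t-test. It does not remove the point, because no other planned analysis of dependence addresses the family and peer objectives separately. The t-test outcome is inferred, but the argument about the ANOVA does not need it.

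Second, the harm is entirely assumed. The Background names parental smoking, family disputes, supervision, hostel life and social acceptance as drivers, not age, gender, college or year. The chi-square analysis shows only that the authors will look for links. The sample could also be smaller than those used here if only nicotine users are analysed: setting A at N = 100 gives about 8%. And if non-users are scored, many values may sit at zero, which normal errors do not represent. All of this stands: the omission is certain, but its effect may be negligible.

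Third, the return to 5% is built into the simulation, since gender is its only confounder. In a one-time survey, unmeasured factors remain, as does reverse causation: dependence may strain family relations, and users may choose friends who use. This too stands. Adjustment removes an avoidable bias from measured variables and no more.

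**Conclusion.** The concern holds. The plan collects four demographic variables in a non-randomised survey and uses none of them in either analysis of dependence. The main-effect contrasts are exposed to confounding, and so is the t-test when the demographic variable is related to family functioning. The interaction test is largely safe provided the demographic effect is additive.

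The size cannot be determined from the documents. With moderate assumed confounding by gender alone, a test with no true effect behind it rejects two to more than four times as often as it should, and a larger sample makes this worse. With weak confounding the effect is trivial. The change is worth making because the gap is certain and closing it costs little. The documents do not show that the results will in fact be materially biased.

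**What to change.** Pre-specify as the main analysis of the Fagerström score a linear model (ANCOVA) with family functioning, peer pressure and their interaction, adjusted for gender, age, year of study and college. Enter college as a fixed effect if several colleges are sampled, and state whether year is categorical. Take the functional against dysfunctional contrast among peer-pressured students from this model, and name its outcome. Report the unadjusted ANOVA and t-test as secondary.

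Do not adjust by default for hostel residence or parental smoking, which the Background mentions. They may be part of the exposures or act through them, and they are not among the listed demographic items. At most they belong in a sensitivity analysis, which would need added questions.

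State that adjusted results are associations in cross-sectional data. A model for the mean score also does not directly answer the objective phrased as a likelihood of addiction.

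The core change is SAP wording only: the covariates are collected and SPSS, the named software, fits the model. The cost is a few degrees of freedom, namely one each for gender and for linear age, plus one fewer than the number of years and of colleges. The number of colleges is not stated, so the total cannot be fixed now. Age and year will overlap, so their own coefficients should not be interpreted.

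### The smoking-status chi-squares ignore college and class: the year-of-study test may be anti-conservative, and the peer-pressure association may be confounded by college

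*Combined protocol and SAP*

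**What the plan says.** Eligibility (Participants, Inclusion Criteria) is "Student enrolled in medical colleges in South Punjab, willing to participate", so more than one college is in scope. The number of colleges and the sampling method are not given. The exclusion of "Those who were absent" suggests recruitment in class or on site, but the plan does not say so.

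The questionnaire (Data Collection Procedure) records "age, gender, medical college, and year of study". College and the college-by-year class can therefore be identified for every student.

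The Statistical Analysis Plan is a single paragraph with three analyses:
- "A two-way analysis of variance (ANOVA) will be conducted", to examine how family functioning and peer pressure interact in their effect on nicotine dependence
- an independent t-test of functional against dysfunctional families, among students who report peer pressure
- "A Chi-square test will be used to examine associations between gender, year of study, peer pressure, and smoking status"

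College appears in none of them. Year appears only as a factor to be tested. There is no mixed model, GEE, stratified test or design-based chi-square. Normality and equal variances are to be checked; independence, which all three methods require, is not mentioned.

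**The concern.** The Background section names peer pressure, hostel life and social acceptance as drivers of nicotine initiation. Students in one college, and more so in one class, share those influences. A study built on the idea that peers shape each other's smoking has little ground for treating classmates' outcomes as independent.

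Two separate problems follow.

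- **Precision of the year test.** Year is constant within a class. If smoking varies between classes for reasons other than year, an ordinary chi-square reads that variation as a year effect.
- **Confounding of the peer-pressure test.** If some colleges have both more smoking and more peer pressure, a crude table pooled over colleges shows an association even when there is none within any college. The second objective is about peer pressure and nicotine use, so this test bears on it directly.

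**Working it through.** **Inputs.** The documents give only the significance level: "the level of statistical significance will be set at" 0.05. They give no sample size, power, ICC or design effect to reproduce. Everything else here is assumed: five class years (so 4 df for year), the class sizes, the ICCs, five colleges, and 25% smoking in the class-clustering simulations. The chi-square sentence is read as each factor tested against smoking status.

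**1. Year of study (constant within a class).** The design effect is DEFF = 1 + (m - 1) x ICC, with m students per class. The actual type I error is P(chi-square on 4 df > 9.488 / DEFF).

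| m | Class ICC | DEFF | 9.488 / DEFF | Actual type I error |
|---|---|---|---|---|
| 20 | 0.02 | 1 + 19 x 0.02 = 1.38 | 6.88 | 14.3% |
| 20 | 0.05 | 1 + 19 x 0.05 = 1.95 | 4.87 | 30.1% |
| 40 | 0.02 | 1 + 39 x 0.02 = 1.78 | 5.33 | 25.5% |
| 40 | 0.05 | 1 + 39 x 0.05 = 2.95 | 3.22 | 52.2% |

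With 10 students per class and ICC 0.01, the figure is only 6.9%. Simulation with the ICC set on a latent scale gives 9.6% (m = 20, ICC 0.02), 18.6% (m = 20, ICC 0.05) and 33.3% (m = 40, ICC 0.05). These are lower because a latent ICC corresponds to a smaller ICC for the observed yes/no outcome. The direction is the same.

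**2. Year, with clustering by college only.** With years balanced across five colleges, the simulated year test rejects 4.5% (latent college ICC 0.05) and 3.2% (0.20), so it is slightly conservative. With an uneven mix of years across colleges it rejects 7.4% (ICC 0.02) and 11.9% (0.05).

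**3. Factors that vary between classmates.** Here DEFF = 1 + (m - 1) x ICC of factor x ICC of outcome. With m = 20 and outcome ICC 0.05:
- factor ICC 0: DEFF 1.00, type I error 5.0%
- factor ICC 0.05: 1 + 19 x 0.05 x 0.05 = 1.05, type I error about 5.6%
- factor ICC 0.20: 1 + 19 x 0.20 x 0.05 = 1.19, type I error 7.2%

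In simulation the ANOVA interaction rejects 4.5-5.3% and the t-test 4.4-5.4% in every scenario. An extreme case of 80 students per college with ICC 0.10 for both factor and outcome gives 1 + 79 x 0.10 x 0.10 = 1.79 and 14.3%.

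**4. Peer pressure and smoking, confounded by college.** The simulations in step 3 draw the cluster effects on exposure and outcome independently, so they cannot show confounding. With five colleges of 80, no association within any college, latent ICC 0.10 and positively correlated college effects, the crude chi-square rejects about 11-16%. A test stratified by college rejects about 4-6%. The excess shrinks quickly as the ICC or the correlation falls.

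**The case against.** **All p-values are too small.** A reader might infer this from the missing cluster term. The documents do not support it. The ANOVA interaction and the t-test compare students who differ within a class, and they hold close to 5% in simulation. Strong clustering of family functioning, a household attribute, would be needed to change that, and nothing in the documents points to it. If FTND is analysed only in nicotine users (not stated), the effective class or college size, and with it any inflation, is smaller still.

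**College clustering by itself inflates the year test.** This is also tempting and also unsupported. With balanced years the test becomes slightly conservative. Inflation needs variation between classes or an uneven year mix. What remains is that the plan sets no quota or sampling frame that would secure balance.

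**Year of study is in no objective, and every magnitude is assumed.** Both points stand and limit the weight of the concern. They do not touch the peer-pressure test, which does serve an objective.

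**College norms are part of the mechanism, so adjusting for college removes some of what is under study.** This is fair. Adjustment turns the estimate into a within-college association, and the plan should say so.

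**A careless remedy can be worse than the problem.** This is correct. Uncorrected class-level cluster-robust tests of year rejected between 23% and 57% in simulations with three to eight colleges.

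**Conclusion.** The concern holds in limited form. Nesting in colleges is real, the identifiers are collected, and no planned test uses them.

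- **Year of study:** the chi-square is anti-conservative if classmates resemble each other. Actual error is about 14-52%, assuming five years, 20-40 students per class and class ICC 0.02-0.05.
- **Peer pressure:** the crude association with smoking status is open to confounding by college. False rejection is about 11-16%, against about 4-6% when stratified, assuming five colleges of 80, latent ICC 0.10 and correlated college effects.
- **ANOVA interaction and t-test:** little affected, unless family functioning or peer pressure itself clusters strongly.

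These figures show what could happen under stated assumptions and do not estimate this study's error rate. That rate cannot be established without the sample size, number of colleges, class size and ICC. The change is worth making because it is cheap, not because the planned results are shown to be wrong.

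**What to change.** 1. State the sampling method, the number of colleges and the expected number of students per college and year.
2. Add medical college as a fixed factor to the FTND model. The simulations above cover its interaction term, but its peer-pressure main effect is open in principle to the same confounding by college.
3. Replace the separate smoking-status chi-squares by one logistic model with gender, year of study, peer pressure and college.
4. Test year against variation between college-by-year classes. Use either a class random intercept with small-sample degrees of freedom, or a class-level F test with college as a factor; the latter held about 4-6% in simulation. Do not use uncorrected cluster-robust errors.
5. Say that the resulting estimates are within-college associations.

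**Cost.** This is a change of SAP wording, with no new data. The college factor uses one degree of freedom fewer than the number of colleges (four, with five colleges). The year test loses power, because its error term has (colleges - 1) x (years - 1) degrees of freedom: 4 x 4 = 16 with five colleges and five years, and fewer if fewer colleges take part.
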